- Virological criterion: persistently positive SARS-CoV-2 PCR \geq 21 days.

Although 21 days may not be a particularly long duration in this type of patient, in this study we will use this time reference to identify patients with persistent infection.

Current COVID-19 treatment guidelines recommend the use of a single agent within few days of symptoms for all the patients with mild disease but with risk factors for progression

to severe disease, including immunocompromised condition. Remdesivir remains the only approved antiviral to treat hospitalized patients with COVID-19 in case of progression to LRTI and, in any case, after 10 days from diagnosis patients are no longer eligible for any treatment. Moreover, specific indications for immunocompromised patients are limited to the use of long-acting monoclonal antibodies as SARS-CoV-2 pre-exposure prophylaxis for individuals who may have an inadequate immune response to COVID-19 vaccination. It should also be specified that there is currently insufficient evidence to guide clinical recommendations for other treatments in immunocompromised patients [7].

However, in clinical practice, it appears clear that such recommendations are not sufficient to guarantee the cure of SARS-CoV-2 infection in immunocompromised patients, in particular in the “long persisters” population. Currently in literature, only case reports or small case series have described the prevalence and the management of patients with persisting infection. These studies show a wide variability of therapeutic approaches ranging from the adoption of repeated or prolonged cycles of remdesivir [8-10] or nirmatrelvir/ritonavir [11], dual antiviral therapy [12-13] and combination therapy with antiviral and monoclonal antibodies [14-16]. These case reports show variable success rates and highlight the need for larger studies focused on immunocompromised patients, to identify the best therapeutic approach in this population.

With this premise, we would like to conduct an observational study on immunocompromised patients, and specifically on haematological patients with B cell malignancies diagnosed with SARS-CoV-2 infection, with the aims of assessing the prevalence of those with persisting COVID-19, associated risk factors and describe the different clinical managements and their related outcomes.

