3.3 Endpoints

The first primary endpoint variable will be the prevalence of persisting SARS-CoV-2 infection among the immunocompromised patients defined as the persistence or the recurrence of symptoms and signs (fever, dyspnea, hypoxemia, changes on chest-X ray or CT scan) and positive SARS-CoV-2 PCR ≥ 21 days after the time 0 (day of the first test positive for SARS-CoV2 infection).

The endpoints for the secondary objectives are:

- Duration of treatment carried out to address the persistent COVID-19 condition and treatment-related adverse effects.
- Duration of viral shedding, defined as the number of days between the first positive test and first negative PCR test.
- Duration of symptoms, defined as the number of days between symptoms onset and the clinical cure.
- Prevalence of imaging alterations, defined as the presence of new ground-glass and/or crazy paving and/or interstitial infiltrates at chest CT scan during the persisting infection (starting from 21 days after the first positive test until viral clearance).
- Re-infection within 120 days, define as new positive test with or without symptoms after viral clearance has been achieved.
- All-cause 120-day mortality.

4. Investigational plan

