4.8 Statistical Analysis Plan

Patients' characteristics will be summarized using absolute frequencies and percentages (categorical variables) and mean±standard deviation or median and interquartile range (scale variables, according to their distribution).

The prevalence of persisting SARS-CoV-2 infection among the immunocompromised patients will be obtained as the ratio of the number of patients with evidence of persisting SARS-CoV-2 infection on the total number of enrolled patients.

As for the analysis of risk factors for persisting COVID, comparisons between COVID-persistent and non-persistent patients will be carried out by means of survival analyses for all outcomes expressed as durations (time-to-event analyses). These outcomes will be compared by estimating Kaplan-Meier curves, calculating log-rank tests and multiple Cox regressions in which COVID persistence will be the main risk factor and including the confounders and effect modifiers listed below.

- Age
- Sex
- Comorbidities (Charlson Comorbidity Index)
- Underlying hematologic disease state
- Chemotherapy treatments performed
- Duration of Hospital stay
- Admissions to intensive care
- Days with central venous catheter
- Bacterial and fungal superinfections
- Vaccination status
- Previous SARS-CoV-2 infections
- Serological status (anti-SARS-CoV-2 antibodies)

Re-infection and imaging alterations rates will be calculated as the ratio of the number of events to the overall number of patients, and the comparison between persisters and non-persisters will be carried out by calculating the corresponding risk ratios. A multiple logistic regression model will assess the relationship between exposure and re-infection (image alteration) net of the potential confounders.

For secondary aims, the secondary endpoints will be described just for the patients with persisting COVID, categorical variables will be reported as number and relative

frequencies, continuous variables will be reported as mean±SD or median and IQR according with their distribution.

5. Administrative procedures and declarations

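### A symptomatic positive PCR after viral clearance can count as both persistence and re-infection, so in the planned risk ratio the outcome can define the exposure

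*Combined protocol and SAP*

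**What the plan says.** Section 3.3 (Endpoints) sets the primary case definition. It needs "the persistence or the recurrence of symptoms and signs" (fever, dyspnea, hypoxemia or imaging changes) together with a "positive SARS-CoV-2 PCR ≥ 21 days after the time 0". It does not ask that PCR stayed positive in between, and the definition itself has no closing date.

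The same section defines re-infection within 120 days as a "new positive test with or without symptoms after viral clearance has been achieved". Viral clearance is not defined. The nearest marker is the shedding endpoint, the "number of days between the first positive test and first negative PCR test".

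Three other places imply a boundary between the two events:
- Section 2.1 gives the virological criterion as "persistently positive SARS-CoV-2 PCR" for at least 21 days.
- The imaging endpoint in 3.3 treats the persisting infection as running from day 21 up to clearance.
- Section 4.4.1 takes only a patient's first infection in the study period and assigns re-infection to the secondary endpoints.

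Section 4.8 divides re-infections by all patients and says that "the comparison between persisters and non-persisters will be carried out by calculating the corresponding risk ratios". A logistic model for confounders follows.

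**The concern.** Take a patient who clears the virus on day 12 and on day 70 has fever and a positive PCR. Under 3.3 this is a recurrence of symptoms with a positive PCR after day 21, so the patient is a persister. It is also a new positive after clearance within 120 days, so the patient has a re-infection. No hierarchy, minimum interval or sequencing rule decides between the two.

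In the section 4.8 comparison, such a patient leaves the non-persister group because of the re-infection and is then counted as an event among the persisters. Adjusting for confounders cannot remove this, because the event itself sets group membership. The same grouping also feeds the primary prevalence and the other persister versus non-persister comparisons, including 120-day mortality. Different centres could code the same patient differently.

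**Working it through.** **The plan's own figures.** Section 4.4.3 expects 1,000 patients, about 300 of them with prolonged infection: 300/1,000 = 30.0%. Its mortality sample size also reproduces. For survival 0.97 v 0.93 and allocation k = 0.43, HR = ln 0.93/ln 0.97 = 2.383. Then E = (1.960 + 0.842)² × [(1 + 0.43 × 2.383)/(1 − 2.383)]²/0.43 = 39.1, and N = 39.1/0.04203 ≈ 931, against 933 stated. This point does not challenge that calculation. The plan gives no rate, sample size or power for re-infection.

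**Inputs for the illustration**
- From 4.4.3: N = 1,000, P = 300 persisters, 700 non-persisters.
- Assumed: re-infection risk r = 5% in both groups, so the true risk ratio is 1.0.
- Assumed: a share q = 40% or 60% of re-infections in non-persisters is symptomatic, falls at day 21 or later, and is coded as persistence as well as re-infection.

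**Formulas**
- Patients moved: m = 700 × r × q
- Apparent prevalence = (300 + m)/1,000
- Apparent risk ratio = [(300r + m)/(300 + m)] ÷ [(700r − m)/(700 − m)]

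**Results at r = 5%** (15 true events in persisters, 35 in non-persisters)

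| | q = 40% | q = 60% |
|---|---|---|
| Moved | 14 | 21 |
| Persisters | (15 + 14)/314 = 29/314 = 9.2% | (15 + 21)/321 = 36/321 = 11.2% |
| Non-persisters | (35 − 14)/686 = 21/686 = 3.1% | (35 − 21)/679 = 14/679 = 2.1% |
| Risk ratio | 3.0 | 5.4 |
| Prevalence | 31.4% | 32.1% |

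**Sensitivity to the assumptions**
- With r = 3% or 8% and q = 40–60%, the ratio is 2.9–5.7.
- With r = 1–10% and q = 25–75%, the ratio is 1.9–10.7 and prevalence rises by 0.2–5.3 percentage points.
- With 150 true persisters instead of 300, over that wider range, the ratio is 2.8–20.0 and prevalence rises by 0.2–6.4 points.

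**What the illustration leaves out**
- *Relapse.* If the later positive is a relapse of the first infection, the patient is rightly a persister and prevalence is correct. The re-infection count is then wrong. The surplus events still fall only among persisters, so the ratio is still pushed up.
- *Time at risk.* A patient still positive on day 21 has at most 120 − 21 = 99 days left in which to be re-infected. One who cleared on day 12 has 120 − 12 = 108. Section 4.8 uses no person-time, so this pulls the ratio down.

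**The case against.** The strongest reply is that the protocol already implies the boundary. The imaging endpoint ends the persisting infection at clearance, re-infection starts after clearance, and 4.4.1 limits attention to the first infection. Read together, the two states are consecutive, and the patient in the example is not a persister if day 12 was clearance. This shows what was intended. But neither clause is carried into the primary definition, which is the text that will be used to classify patients, so the overlap stands.

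Several stronger readings are tempting, and the documents do not support them:
- *Every re-infection counts twice.* Only a positive that follows clearance, falls at day 21 or later and comes with a qualifying symptom or sign can do so. Other new positives are re-infection only.
- *One negative PCR is clearance.* That is an inference from the shedding endpoint; clearance is undefined.
- *Persistence is open-ended.* The definition has no upper limit, but section 4.5 ends follow-up at 120 days.
- *Prevalence is necessarily inflated.* It is not if the event is a relapse, and section 2.1 describes viral rebound and relapsing symptoms in these patients.

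It is also fair to say that the 1.4–2.1 point shift is smaller than the sampling half-width for 30% of 1,000, which is 1.96 × √(0.3 × 0.7/1,000) = 2.8 points. Unlike sampling error, however, this bias does not shrink with more patients.

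**Conclusion.** The concern holds as an overlap of definitions that biases a stated analysis. A symptomatic positive after clearance, at day 21 or later, can be both the exposure and the outcome, against the intent of 2.1, the imaging endpoint and 4.4.1.

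The ratio of 3.0–5.4 and prevalence of 31.4–32.1% illustrate this mechanism alone. They rest on an assumed re-infection risk, an assumed symptomatic share, a true ratio of 1.0, and every such event being a new infection coded both ways. A reader might infer that the reported ratio will be too high by that factor. The documents do not support this: the time-at-risk bias runs the other way, its size is not given, and the net bias is unknown. As planned, the ratio cannot be interpreted in either direction.

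This is a should-fix, not a must-fix: the large effect is on a secondary endpoint and the effect on the primary prevalence is modest.

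**What to change.** 1. In 3.3, define viral clearance explicitly. At present only the end of shedding is defined, by the first negative PCR.
2. In 3.3, require the qualifying positive PCR at day 21 or later to occur before clearance, with recurrence meaning symptoms within that same uncleared episode. Count any positive after clearance only as re-infection. The two are then mutually exclusive, and persistence status is settled by the time a patient clears.
3. In 4.8, analyse re-infection only among patients who reached clearance, with time at risk starting at clearance, instead of dividing by all patients. This also deals with the shorter time at risk in persisters.
4. Add one sensitivity analysis with a pre-stated interval within which a positive after a negative is treated as the same episode.

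The cost is a few sentences in 3.3 and 4.8 and one extra analysis. PCR dates are already needed for the shedding endpoint. The downside is that some relapses may be labelled re-infection in the main analysis; the sensitivity analysis shows how much that matters.

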4.1 Study type

- Cross-sectional study
- Retrospective Case-control study
- Retrospective cohort study
- Prospective cohort study
- Retrospective and prospective cohort study
- Descriptive pilot/feasibility study
- Qualitative study

4.2 Mono or multicenter study

- Monocentric
- National multicenter
- International multicenter

4.2.1 Multicenter study coordination

Alma Mater Studiorum – University of Bologna (UNIBO), Department of Medical and Surgical Sciences is the promoter of this study. The clinical center affiliated to UNIBO, which is the Infectious Disease Unit, IRCCS Azienda Ospedaliero-Universitaria di Bologna (IRCCS AOU of Bologna) Policlinico di Sant'Orsola, will be the coordinator center. Other clinical centers will be invited to share their data under the terms and conditions described in this protocol.

4.3 Study design

Spontaneous international multicenter retrospective and prospective observational study.

The retrospective recruitment period will span from 1.01.2022 to the date of authorisation by hospital directorates following the Ethics Committees' approvals. This period has been established considering the prevalent diffusion of the omicron variant and its subvariants, which has led to significant changes in the clinical manifestations of COVID-19. The prospective recruitment will be carried out over the 12 months immediately following the retrospective period.

During the study period, screening for persisting SARS-CoV-2 infection and therapeutic management of all patients will be carried out by the attending physicians according to routine practice.

4.4 Study population

All immunocompromised adults (≥ 18 years) with a new SARS-CoV-2 infection assessed during the study period, hospitalized or followed as outpatients in the Haematological Units of the participating centers, will be screened for inclusion.

4.4.1 Inclusion Criteria

- Diagnosis of B cell malignancies or previous treatment with B cell targeting therapies.
- Diagnosis of proven SARS-CoV-2 infection confirmed by a PCR test (only the first infection during the study period will be considered, re-infection will be counted as a secondary endpoint).
- Provision of signed and dated informed consent.

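### No window is set for the confirming PCR or first centre contact, so entry can depend on still being infected at day 21, which can inflate the primary prevalence

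*Combined protocol and SAP*

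**What the plan says.** - **Eligibility (4.4.1, 4.4.2).** The infection criterion is "Diagnosis of proven SARS-CoV-2 infection confirmed by a PCR test". No interval from the first positive test is given, and there are no exclusion criteria.
- **Population (4.4).** Adults "with a new SARS-CoV-2 infection assessed during the study period" who are "hospitalized or followed as outpatients in the Haematological Units of the participating centers, will be screened for inclusion". The word new has no day limit, and no latest day is set for first contact with the unit.
- **Primary endpoint (3.3).** A case needs persistent or recurrent symptoms or signs and a "positive SARS-CoV-2 PCR ≥ 21 days after the time 0 (day of the first test positive for SARS-CoV2 infection". The later test must be a PCR; the test that defines time 0 is not specified.
- **Shedding endpoint (3.3).** The duration is "the number of days between the first positive test and first negative PCR test", which again names PCR for the later test only.
- **Testing (4.3).** Screening for persistence "will be carried out by the attending physicians according to routine practice". No PCR is mandated at baseline or at day 21.
- **Estimator (4.8).** Prevalence is "the number of patients with evidence of persisting SARS-CoV-2 infection on the total number of enrolled patients".

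**The concern.** Take two patients whose first positive test on day 0 is not a PCR. One recovers by day 8, never has a PCR and cannot be enrolled. The other is still symptomatic and has a first positive PCR on day 25. That single result meets the inclusion criterion and, with the symptoms, the case definition. Eligibility has then depended on the outcome.

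First contact opens a second route. A patient diagnosed elsewhere may come to a participating unit only because the infection is prolonged. A similar patient who cleared elsewhere may never appear in the unit's records.

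The primary objective is a prevalence with its risk factors. If persisters have entry routes that patients who clear do not have, the denominator is short of non-cases, and enrolling more patients under the same rules does not correct that.

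**Working it through.** **1. The plan's own figures.** Section 4.4.3 assumes about 30% prolonged infections: 0.30 × 500 = 150 at the coordinating centre and 0.30 × 1,000 = 300 overall, as stated. That 30% refers to viral shedding alone, without the symptom component of the endpoint, so it serves here only as a reference value. The 95% half-width is 1.96 × √(0.3 × 0.7 / 1,000) = 2.8 points, giving an interval of 27.2% to 32.8%.

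**2. Direction of the PCR route.** Every counted persister has a positive PCR by definition; a patient who clears may have none. The PCR criterion can therefore remove non-cases but never a counted case. Let p be the true prevalence, g the share of infections first positive on another test with no early PCR, and r the chance that such a non-persister still gets a positive PCR before clearing. If all persisters are tested at day 21 or later:

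observed prevalence = p / [p + (1 − p)(1 − g(1 − r))]

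This is never below p, and equals p when g = 0 or r = 1. Neither g nor r is in the documents. With p = 30%:

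| g | r = 0 | r = 0.5 |
|---|---|---|
| 5% | 31.1% | 30.5% |
| 10% | 32.3% | 31.1% |
| 20% | 34.9% | 32.3% |
| 30% | 38.0% | 33.5% |
| 50% | 46.2% | 36.4% |

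For example, at g = 20% and r = 0: 0.30 / (0.30 + 0.70 × 0.80) = 0.30 / 0.86 = 34.9%.

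**3. Removing late qualifiers (both routes).** Suppose k of the 300 persisters, and no non-persister, qualify only at day 21 or later. Without them the prevalence is (300 − k)/(1,000 − k):

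- k = 25: 275/975 = 28.2%, a shift of 1.8 points
- k = 50: 250/950 = 26.3%, a shift of 3.7 points
- k = 100: 200/900 = 22.2%, a shift of 7.8 points

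The shift reaches 2.84 points, the unrounded half-width, when 28.4 = 0.7284k, so at about k = 39 (13% of persisters).

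**4. If the window also removes non-persisters.** With k = 50 and 50 late-qualifying non-persisters (assumed), the result is 250/900 = 27.8%, a shift of 2.2 points. With 117 (one sixth of 700, the same share as 50 of 300), it is 250/833 = 30.0%, no shift.

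**5. The opposing bias.** Let s be the share of true persisters tested at day 21 or later. With r = 0, and with untested persisters enrolled only if they had an early PCR:

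observed prevalence = ps / [ps + (1 − ps)(1 − g)]

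At p = 30% and s = 80%, this gives 24.0% for g = 0, 0.24/0.924 = 26.0% for g = 10%, and 0.24/0.772 = 31.1% for g = 30%. The net error can have either sign.

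**The case against.** The inclusion wording can be read as PCR at diagnosis, in which case the PCR route closes. The documents mention no antigen or self-tests and describe no referral for prolonged infection. A reader might infer that the plan accepts a first test of any kind and a PCR at any later date; that reads silence as a rule. What stands is that 3.3 names PCR for the later test and not for time 0, twice, and that 4.4.1 gives no date limit. Even with PCR at diagnosis, nothing in 4.4 or 4.4.2 limits late first contact.

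The background in 2.1 speaks of persistently positive PCR, which one first PCR on day 25 would not obviously show. But the endpoint in 3.3, which governs the count, asks only for a positive PCR from day 21 and does not require an earlier one.

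It is also fair that the removal formula in step 3 is one-sided. Under 4.4.1, a patient with a first PCR on days 8 to 20 who then clears is enrolled, as is one with a late positive PCR but no symptoms or signs. Neither is a case, and a narrow window could remove both; step 4 shows how far this shrinks the shift.

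Finally, a restricted set has costs. It may select on access to testing. Section 4.8 also places the time-to-event comparisons under the risk-factor heading, so a loosely worded restriction could shrink the mortality comparison. Removing 100 patients would leave 900, below the 933 tabulated in 4.4.3 for 97% versus 93% survival. This objection stands, and the remedy has to name the analyses it covers.

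**Conclusion.** The gap is real and touches the primary endpoint. Followed as written, the rules let a PCR or first contact at day 21 or later serve both entry and case status, and they can exclude non-cases without ever excluding a counted case. Taken alone, the mechanism raises the prevalence or leaves it unchanged; for the contact route, this assumes that prolonged infection makes late contact no less likely.

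A reader might go further and conclude that the reported prevalence will be too high. The documents do not support that. The effect is nil if all patients have an early PCR and early contact, and incomplete day-21 testing pulls the other way. Nor do they show how the effect varies by centre or period.

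The size is unknown. The shift from 30.0% to 28.2%, 26.3% or 22.2% is an illustration that assumes no non-persister qualifies late; only then does it pass sampling error at about 39 patients. The power table is unaffected except through its assumed 300/700 split.

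**What to change.** - **3.3 and 4.4.1.** State which test type defines time 0. Record the type and date of the first positive test, the date of the confirming PCR and the date of first contact with the centre.
- **4.8, prevalence and its risk factors.** Estimate these in patients whose confirming PCR and first centre record both fall within a pre-specified early window from time 0, well before day 21. Apply the window identically to persisters and non-persisters, and report the result beside the all-enrolled prevalence.
- **4.8, everything else.** Say explicitly that the full cohort is kept for mortality, the other outcome comparisons and the description of management.

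The cost is one definition, one analysis-set clause, one extra reported estimate and a few dates that should be obtainable from the charts and hospital records named in 4.7. The prevalence set will be smaller and its estimate slightly less precise, and it may be selected on early access to testing; showing both figures makes that visible. The window does not correct missed testing at day 21, so the direction of that error should be stated with the result.
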